4.2 Secondary Endpoints

1. Incidence of adverse events (serious and device- and/or procedure-related) to 24 hours post-operative.
2. Incidence of adverse events (serious and device- and/or procedure-related) between 24 hours and 28 days post-operative.
3. Technical success defined as successful occlusion of the treated site as seen on post-embolization angiography.
4. Incidence of device observations relating to EmboCube.

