6.3 Procedural Information

All procedures should be conducted in accordance with site standard of care and patient needs, there are no prohibited concomitant treatments. EmboCube Embolization Gelatin shall be used in accordance with the IFU.

Data collected will include the following:

- Procedure type
- Treated vessel and treated area
- Occlusion of the target area as seen on post-embolization angiography
- Time to hemostasis (TTH) post-EmboCube embolization
- EmboCube Embolization Gelatin size, type and number of units used
- Additional embolic agents used in procedure (e.g., coils, glue, microspheres) - number and type and whether used pre- or post EmboCube
- Transfusion/ use of blood products
- Coagulation status (PT, PTT, INR)
- Repeat embolization or additional surgery to address bleeding within 24 hours
 - Rebleeding due to treated vessel
- Serious and device and/or procedure related adverse events
- Device observations – any observations relating to handling and delivery of EmboCube
- Concomitant anticoagulants and antiplatelet medications

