7.4.3 Device Failures and Malfunctions

All device observations / performance issues, malfunctions, or failures, whether or not associated with an adverse event must be reported to the Sponsor within 24 hours of knowledge of the event or by the end of the next working day. This may be done via eCRF or by phone, fax, or email using the contact

details provided separately to sites.

The Sponsor will review all reported events for potential reporting in accordance with the requirements of Regulation (EU)2017/745 of the European Parliament and of the Council of 5 April 2017 on Medical Devices (MDR), and any applicable guidance(s). The Sponsor may request medical record documentation (e.g., procedure notes, operative notes, discharge summary, relevant progress notes, imaging, or lab studies) to facilitate this review.

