9 STATISTICAL ANALYSIS

The analysis of the data from this study will be primarily descriptive. Continuous endpoints will be summarized by N, mean, standard deviation, median, minimum, and maximum. Categorical or binary endpoints will be summarized by N and percentage with confidence intervals as appropriate. Kaplan Meier plots will be used to display and summarize time to event data.

The planned sample size for analysis is at least 100 subjects which is believed to be adequate to provide an accurate characterization of EmboCube in a "real-world" clinical setting.

Analysis Population

- *Intention-to-Treat (ITT) Analysis Set:* includes all enrolled subjects.
- *Per-Protocol (PP) Analysis Set:* includes all enrolled subjects who met all inclusion/exclusion criteria with no major protocol deviations. This is a secondary analysis set for the primary safety and effectiveness endpoints, as well as secondary endpoints.

While ITT is intended as the primary analysis set for all safety and effectiveness endpoints, the primary safety and effectiveness endpoints will additionally be evaluated in the PP analysis sets as supportive information. All subjects excluded from ITT analysis set will be described.

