11.2 Reporting Timelines

The Investigator will report information and events according to the timelines below:

Form/Report	Submission Timeframe
eCRF	Completion within 10 working days of visit/follow-up, or chart review.
All serious and potentially device-related events and all deaths	Submit notification to Sponsor within 24 hours of the site becoming aware of the event, or by the end of the next working day; submit to the local EC/IRB as required according to local and national regulations.
All device observations / performance issues, malfunctions or failures	Submit notification to Sponsor within 24 hours of the site becoming aware of the event, or by the end of the next working day; submit to the local EC/IRB as required according to local and national regulations.
Major deviations	Submit notification to Sponsor within 24 hours of the site becoming aware of the event, or by the end of the next working day; submit to the local EC/IRB as required according to local and national regulations.
Progress Reports	As required by the local EC/IRB
Final Report to the EC/IRB	As required by the local EC/IRB

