- the event involves a body-site or organ that
 - the study device or procedures are applied to;
 - the study device or procedures have an effect on;
- the serious adverse event follows a known response pattern to the medical device (if the response pattern is previously known);
- the discontinuation of medical device application (or reduction of the level of activation/exposure) and reintroduction of its use (or increase of the level of activation/exposure), impact on the serious adverse event (when clinically feasible);
- other possible causes (e.g., an underlying or concurrent illness/ clinical condition or/and an effect of another device, drug, or treatment) have been adequately ruled out;
- harm to the subject is due to error in use;

In order to establish the relatedness, not all the criteria listed above might be met at the same time, depending on the type of device/procedures and the serious adverse event.

ADVERSE EVENT SEVERITY

The following definitions for rating severity of adverse events will be used:

Mild: Awareness of signs or symptoms, but easily tolerated; are of minor irritant type; causing no loss of time from normal activities; symptoms would not require medication or a medical evaluation; signs or symptoms are transient.

Moderate: Interferes with the subject's usual activity and/or requires symptomatic treatment.

Severe: Symptom(s) causing severe discomfort and significant impact of the subject's usual activity and requires treatment.

Device Failure: A device that is used in accordance with the Instructions for Use, but the device does not perform according to the Instructions for Use and negatively impacts the treatment.

Device Malfunction: A malfunction of a device is an unexpected change to the device that is contradictory to the Instructions for Use and may or may not affect device performance.

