3 STUDY SYNOPSIS

Study Title:	A Multicenter Observational Study to Evaluate Outcomes of EmboCube Embolization Gelatin to Control Bleeding or Hemorrhage
Study Objective:	To collect clinical safety and performance outcome data associated with the use of EmboCube Embolization Gelatin (EmboCube) to control bleeding or hemorrhage
Study Device:	EmboCube™ Embolization Gelatin
Study Design:	Multicenter observational post-market ¹ clinical follow-up study in subjects treated with EmboCube
Device Regulatory Status:	European Union: CE mark approved March 2019 (CE 667862) Australia: Investigational device
Sample size:	A minimum of 100 subjects will be included. This sample size is based on a one-sample non-inferiority analysis of clinical success based on the parameters listed below and a 15% loss-to-follow-up: 
 • Reference Clinical Success rate (p_0): 92%* • Treatment rate (p): 90% • Non-inferiority margin: 10% • α: 0.05 • Power: 80% *The reference Clinical Success rate is based on historical clinical literature data for benchmark gelatin-based embolic devices
Subject Population:	Subjects who are treated with EmboCube to control bleeding or hemorrhage in accordance with the current approved CE Mark indication for use as stated in the Instructions for Use (IFU)
Clinical Sites:	Up to 7 centers may be included to allow enrollment of required subjects
Study Follow-Up:	Data will be collected to 28 days post-procedure
Estimated Study Duration:	First patient enrolled: July 2022 Last patient enrolled: July 2023 Last patient, last visit: August 2023
Primary Endpoints:	The primary performance endpoint will be clinical success defined as cessation of bleeding post-embolization and absence of re-bleeding at the treated site requiring re-intervention (i.e., repeat embolization or additional surgery) within 24 hours The primary safety endpoint will be absence of unanticipated serious adverse device effects within 24 hours
Secondary Endpoints:	1. Incidence of adverse events (serious and device and/or procedure-related) to 24 hours post-operative 2. Incidence of adverse events (serious and device- and/or procedure-related) between 24 hours and 28 days post-operative

	
 3. Technical success defined as successful occlusion of the target area as seen on post-embolization angiography 4. Incidence of device observations related to EmboCube

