8.3 SECONDARY DATA ANALYSES

All secondary endpoints will be tabulated. Means, SDs, and sample size will be used to summarize continuous variables. Distributions of continuous data will be examined and if non-normality is exhibited, medians and interquartile ranges will be presented. Frequencies and percentages will be used to summarize categorical variables. All available data will be used for each endpoint and no imputations will be performed.

Incidence of adverse events to 24 hours post-operative (serious and device- and/or procedure-related)

Endpoint Derivation:

- Serious adverse events as reported by the site, **AND**
- “Seriousness” is checked as anything other than “Not Serious”, **AND**
- Relationship to study device **AND/OR** relationship to study procedure is “Definitely related”

Incidence of adverse events between 24 hours and 28 days post-operative (serious and device- and/or procedure-related)

Endpoint Derivation:

- “Were there any serious and device- or procedure-related adverse events since the 24-hour contact visit?” is checked YES, **AND**
- Serious adverse events as reported by the site and in which “Seriousness” is checked as anything other than “Not Serious”, **AND**
- Relationship to study device **AND/OR** relationship to study procedure is “Definitely related”

Technical success defined as successful occlusion of the treated site as seen on post-embolization angiography

Endpoint Derivation:

- “Was occlusion of the treated area (as seen on post-embolization angiogram) successful?” is checked YES

Incidence of device observations related to EmboCube

Endpoint Derivation:

- “Was procedure aborted due to device observation?” is checked YES

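### SAP 8.3 counts only aborted procedures as device observations, so the secondary-endpoint rows would show an abort rate under the observation label

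*SAP*

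**What the plan says.** The endpoint is named without any abort condition in the Protocol Summary and Protocol 4.2 ("Incidence of device observations relating to EmboCube") and in SAP 3 and SAP 7.2 ("Incidence of device observations related to EmboCube"). The sub-heading in SAP 8.3 and the table titles in SAP 9.1 carry the same unrestricted label.

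Protocol 6.3 sets what sites record as a device observation: "any observations relating to handling and delivery of EmboCube". Protocol 7.4.3 adds a reporting duty: "All device observations / performance issues, malfunctions, or failures, whether or not associated with an adverse event must be reported to the Sponsor". The table in Protocol 11.2 repeats that scope: "All device observations / performance issues, malfunctions or failures".

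SAP 8.3 then gives the derivation. It has one criterion, that "Was procedure aborted due to device observation" is checked YES, and no other item is combined with it.

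SAP 9.1 places the endpoint in both the ITT and the PP secondary-endpoint tables. SAP 9.1 and 9.2 also list a separate ITT table and a listing for device observations, without describing their content. SAP 8.1 gives categorical endpoints a Clopper-Pearson 95% interval and bases percentages on subjects whose value is not missing.

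**The concern.** An abort caused by an observation is one possible consequence of an observation. The endpoint asks how often observations occur, but the derivation counts only those that ended the procedure. If a syringe is hard to prepare or delivery is difficult and the operator still completes the embolization, the subject has an observation under Protocol 6.3 and none under SAP 8.3.

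This is the only secondary endpoint on handling and delivery of the device. Protocol 1.5 says the study data will feed product risk analysis, the clinical evaluation report and possibly the labelling. SAP 8.1.5 foresees interim analyses for regulatory submissions. A reader of those outputs would take the row at its label, with an exact confidence interval beside it, when both describe the abort rate. The separate device-observation table could also show a different figure from the endpoint row in the same report.

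**Working it through.** The plan gives no expected rate, precision or power for this endpoint, so there is no stated figure to reproduce. The check compares the texts and then illustrates the arithmetic.

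**Step 1: definition against derivation.**

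| Place | What counts |
|---|---|
| Protocol Summary and 4.2; SAP 3 and 7.2 | Device observations, no abort condition |
| Protocol 6.3 | Any handling or delivery observation |
| Protocol 7.4.3 and 11.2 | All observations, reported whatever the outcome of the procedure |
| SAP 8.3 | Only observations that led to an abort |

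Nothing in either document redefines an observation as an abort. Where SAP 8.3 needs several items for an endpoint, it joins them explicitly with AND; here there is nothing to join. Nor does the protocol assume that device problems end the procedure: Protocol 12 describes a malfunction as a change that is "contradictory to the Instructions for Use and may or may not affect device performance".

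**Step 2: relation between the two counts.** Let N be the subjects analysed, D those with at least one EmboCube observation, and A those whose procedure was aborted because of one. Then 0 ≤ A ≤ D. With all N subjects in the denominator:

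- named incidence = D/N
- reported figure = A/N
- reported ÷ named = A/D
- shortfall = (D − A)/N

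The two agree only if A = D.

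**Step 3: illustration.** N = 100 is the planned minimum (SAP 5.5). Every value of D and A is an assumption. Intervals are Clopper-Pearson 95%, as in SAP 8.1.

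| D | A | Named incidence (95% CI) | Reported (95% CI) | Shortfall, points |
|---|---|---|---|---|
| 5 | 0 | 5% (1.64 to 11.28) | 0% (0 to 3.62) | 5 |
| 5 | 1 | 5% (1.64 to 11.28) | 1% (0.03 to 5.45) | 4 |
| 5 | 5 | 5% (1.64 to 11.28) | 5% (1.64 to 11.28) | 0 |
| 10 | 1 | 10% (4.90 to 17.62) | 1% (0.03 to 5.45) | 9 |
| 10 | 2 | 10% (4.90 to 17.62) | 2% (0.24 to 7.04) | 8 |
| 10 | 5 | 10% (4.90 to 17.62) | 5% (1.64 to 11.28) | 5 |
| 10 | 10 | 10% (4.90 to 17.62) | 10% (4.90 to 17.62) | 0 |
| 20 | 2 | 20% (12.67 to 29.18) | 2% (0.24 to 7.04) | 18 |
| 20 | 5 | 20% (12.67 to 29.18) | 5% (1.64 to 11.28) | 15 |
| 20 | 20 | 20% (12.67 to 29.18) | 20% (12.67 to 29.18) | 0 |

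Whether the reported interval still contains the named rate depends on the case. With D = 5 and A = 1 it does (upper limit 5.45%), and with D = 10 and A = 5 it does (11.28%). With D = 10 and A = 2 it does not (7.04%).

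**Step 4: the denominator.** SAP 8.1 uses subjects with a recorded value. If the eCRF asks the abort question only after an observation has been entered, the percentage becomes A/D. With D = 10 and A = 2 that is 2/10 = 20%, against a named incidence of 10/100 = 10%. The count A still cannot exceed D, but the percentage could then overstate the incidence. The eCRF is not among the documents, so this cannot be settled from them.

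**The case against.** The strongest reply is that little is lost. Sites must report every observation to the sponsor, a separate ITT table and a listing are planned, and Protocol 9 says "The analysis of the data from this study will be primarily descriptive". The sample size rests on clinical success, and no test or decision uses this endpoint. All of that is correct and limits the weight of the point. It does not correct the endpoint row. The content of the separate outputs is unspecified, and SAP 9.1 lists no PP version of the device-observation table.

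A second reply is that the direction of error is not certain, because the SAP's rule on missing values might make the percentage a share of observations. This also stands: understatement is assured for the count, and for the percentage only when all ITT subjects form the denominator. The other branch is no defence of the derivation, since a share of observations is not an incidence either.

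Third, under Protocol 5.3 a subject consented beforehand who never receives EmboCube is a screen failure with no data collected. A procedure abandoned before any device is delivered would then be missing from both A and D. That limits what any version of this endpoint can show, but it lies outside the ITT set and does not affect the mismatch within it.

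**Conclusion.** The concern holds. Followed as written, SAP 8.3 fills the ITT and PP rows for device observations with the number of procedures aborted because of one. This is a wrong derivation, not a missing detail, and the texts alone establish it.

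Its size cannot be computed from the documents. With all ITT subjects as denominator, the shortfall runs from nothing, if every subject with an observation had an abort because of it, to the whole incidence, if none did. The figures in the illustration rest on assumed counts. The consequence is one mislabelled descriptive row and its interval. It should be corrected before analysis, but it does not affect the primary endpoints or any formal conclusion.

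**What to change.** In SAP 8.3, derive the endpoint as the number and percentage of subjects with at least one recorded EmboCube device observation, with the Clopper-Pearson 95% interval already planned, in the ITT and PP tables already listed. Show procedures aborted because of an observation as a labelled sub-row. State the denominator explicitly, as all subjects in the analysis set or those with a recorded answer to the any-observation item. Say what the separate device-observation table contains, so that it agrees with the endpoint row. It would also help to state whether malfunctions and failures, which Protocol 7.4.3 lists beside observations and Protocol 12 defines, count toward the endpoint; this is a clarification and separate from the error.

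The cost is a short edit to one derivation, with no new table and no protocol change. It uses data that Protocol 6.3 and 7.4.3 already require, subject to confirming that the eCRF has an item recording any observation. The drawback for the sponsor is that the reported rate may look less favourable.

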8.4 SAFETY SUMMARY

All device or procedure-related adverse events collected will be summarized cumulatively throughout the follow-up period. The frequency count of adverse events and the unique number of subjects who had the adverse events will be presented. Also, the frequency and percentage of patients who had a serious adverse event, or a device- or procedure-related serious adverse event will be tabulated separately. If a patient experienced multiple adverse events, only the most severe event or the most intense relationship to the study device will be counted within an adverse event code. The following information will be reported as listings about each adverse event:

- Start date
- Stop date
- Severity
- Relationship
- Action taken
- Outcome

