6 DATA COLLECTION PROCEDURES

6.1 Visit Schedule

Study participation will last for a total of 28 days (+14 days). Follow-up will be by clinic visit or telephone according to site standard of care. Data will be collected from available medical records for baseline, index hospitalization, and standard of care follow-up until 28 days post-procedure. If there is no routine clinic visit or follow-up between 4 and 6-weeks post procedure (28 days +14 days) subjects will be contacted by telephone during this time to collect safety follow-up to 28 days.

A summary schedule of the data collection for tests and evaluations is in Table 1. Data will only be collected if tests and evaluations are completed per standard of care.

Table 1 Data Collection Schedule

Data	Pre-operative/ baseline	Procedure to 24 hours	28-day follow-up ² (28 to 42 days)
Informed consent ¹	X		
Demographics	X		
Diagnosis, i.e., cause and location of bleeding or hemorrhage	X	X	
Procedural information		X	
Clinical Success		X	
Technical success		X	
EmboCube use (size, type, and amount)		X	
No/type other adjuvant embolics employed		X	
Device and/or procedure related serious adverse events		X	X
Occurrence of re-intervention to control bleeding at the treated site		X	X
Concomitant antiplatelet and anticoagulant medications	X	X	X

¹ Subject will be asked to provide written informed consent for data collection either preoperatively or prior to hospital discharge.

² If subject is not seen by site between 4-6 weeks (28 to 42 days) for clinical visit, subject will be telephoned to collect information on potential device related adverse events and reinterventions.

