7.2 Reportable Adverse Events

For the purpose of this study, events which meet the definition of both serious adverse events and that are potentially device-related and/or procedure-related will be reported.

All deaths will be reported as SAE regardless of Investigator assessment of causality.

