7.3 Events Not Considered Adverse Events

For purposes of this study, there are no specific events which are not considered adverse events. All events which meet the definition of both serious adverse events and that are potentially device-related and/or procedure-related, and all deaths will be reported.

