5.7 VISIT SCHEDULE

Study participation will last for a total of 28 (0/+14) days (i.e., 28 to 42 days). Follow-up will be by clinic visit or telephone according to site standard of care. Data will be collected from available medical records for baseline, index hospitalization, and standard of care follow-up until 28 days post-procedure. If there is no routine clinic visit or follow-up between 4 and 6 weeks post-procedure (28 [0/+14] days) subjects will be contacted by telephone during this time to collect safety follow-up data to 28 days.

A summary schedule of the data collection for tests and evaluations is provided in Table 1. Data from tests and evaluations performed outside of standard of care will not be collected.

Table 1. Data Collection Schedule

Data	Pre-operative/ baseline	Procedure to 24 hours	28 (0/+14) days follow-up ¹
Informed consent ²	X		
Demographics	X		
Diagnosis (i.e., cause and location of bleeding or hemorrhage)	X	X	
Procedural information		X	
Clinical Success		X	
Technical success		X	
EmboCube use (i.e., size, type, and amount)		X	

Data	Pre-operative/ baseline	Procedure to 24 hours	28 (0/+14) days follow-up ¹
No/type of other adjuvant embolic employed		X	
Device- and/or procedure-related serious adverse events		X	X
Occurrence of re-intervention to control bleeding at the treated site		X	X
Concomitant antiplatelet and anticoagulant medications	X	X	X

¹If a subject does not have a clinic visit at the site between 4 and 6 weeks (i.e., 28 to 42 days), the subject will be telephoned to collect information on potential device-related adverse events and re-interventions.

²Subject will be asked to provide written informed consent for data collection either pre-operatively or prior to hospital discharge.

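### The unqualified SAE percentage in SAP 8.4 is in effect 'related SAE or death from any cause' and should be labelled that way

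*SAP*

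**What the plan says.** SAP 8.4 (Safety Summary) asks for two counts: "the frequency and percentage of patients who had a serious adverse event, or a device- or procedure-related serious adverse event will be tabulated separately". One is qualified by relatedness and the other, "the frequency and percentage of patients who had a serious adverse event", is not. Nothing in 8.4 or in the table list in SAP 9.1 says which events the unqualified count contains.

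Protocol 7.2 sets the collection rule: "events which meet the definition of both serious adverse events and that are potentially device-related and/or procedure-related will be reported". It adds one exception: "All deaths will be reported as SAE regardless of Investigator assessment of causality". Protocol 7.3 repeats both parts: "All events which meet the definition of both serious adverse events and that are potentially device-related and/or procedure-related, and all deaths will be reported".

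The data collection schedules agree. The only adverse-event row in Protocol Table 1 (section 6.1) is "Device and/or procedure related serious adverse events", and in SAP Table 1 (section 5.7) it is "Device- and/or procedure-related serious adverse events". The two eCRF questions on adverse events that the SAP cites, for the period to 24 hours (8.2) and from then to day 28 (8.3), also ask only about events that are serious and related.

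**The concern.** A row for patients with an SAE, set beside a row for patients with a related SAE, invites the reader to take the first as SAEs of any cause. The study does not systematically collect what such a figure needs. A non-fatal SAE that the site judges unrelated has no required route into the database.

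The population makes such events plausible. Protocol 1.2 describes patients who may have several comorbidities or major trauma and are often treated as emergencies. The results have real uses: Protocol 1.5 directs them to risk analysis, the clinical evaluation report and labelling, and SAP 8.1.5 plans interim outputs for regulatory submissions and publications. A percentage with an unclear label could be carried into any of these as an SAE rate.

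**Working it through.** The documents state no SAE rate, so there is no figure to reproduce. The check compares what is collected with what is tabulated.

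**Step 1. Which SAEs are captured?**

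| Type of SAE | Captured? | Source |
|---|---|---|
| Judged possibly, probably or definitely related | Yes | Protocol 7.2, 7.3, 12 |
| Causality cannot be assessed | Yes, classed as possible | Protocol 12 |
| Fatal, any causality | Yes | Protocol 7.2, 7.3 |
| Non-fatal, judged not related | Not systematically | Protocol 7.2, 7.3; Table 1 in both documents; eCRF questions in SAP 8.2 and 8.3 |

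**Step 2. What does each row of SAP 8.4 then contain?**

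- Unqualified row: patients with a related SAE, plus patients who died of any cause.
- Related row: patients with a related SAE.

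If *related* covers every category from possible upward, the two rows differ only by patients whose sole reportable event is an unrelated death. SAP 8.4 does not say which causality categories count. SAP 8.3 counts only definitely related events for the secondary endpoints, whereas Protocol 7.2 reports potentially related ones.

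**Step 3. Direction of the error if the row is read as an overall SAE rate.** Let *c* be the number of patients captured, *u* the number whose only SAEs are non-fatal and unrelated, and *N* the denominator.

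- Row shown = c / N
- Overall SAE rate = (c + u) / N
- Share of the overall rate shown = c / (c + u)

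Since u cannot be negative, the share cannot exceed 1. It equals 1 only when u = 0.

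**Step 4. Illustration.** N = 100 is the planned minimum (SAP 5.5). The values of c and u are assumptions, because the documents give neither. With c = 10 the table shows 10/100 = 10.0% (Clopper-Pearson 95% CI 4.9% to 17.6%).

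| u (assumed) | Overall rate | Share shown |
|---|---|---|
| 0 | 10% | 10/10 = 100% |
| 5 | 15% | 10/15 = 67% |
| 10 | 20% | 10/20 = 50% |
| 20 | 30% | 10/30 = 33% |
| 30 | 40% | 10/40 = 25% |

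For u from 5 to 30, c = 5 gives shares from 5/10 = 50% down to 5/35 = 14%, and c = 15 gives 15/20 = 75% down to 15/45 = 33%. The range is this wide because it reflects the assumptions alone. The confidence interval gives no protection, since it covers sampling error and not events that were never recorded.

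**The case against.** The best defence is that both counts are right under the protocol's own rules. Deaths are reported as SAEs whatever their cause, so there is a good reason for two rows: related SAEs plus unrelated deaths in one, related SAEs alone in the other. SAP 8.4 never says *any* or *all-cause*, no table shell fixes the row label, and relationship will appear in the listing for each event. This stands in part. The counts are sound; what is missing is a label that says what the first one counts.

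It can also be argued that the paragraph is already limited to what was collected, since it opens "All device or procedure-related adverse events collected will be summarized cumulatively throughout the follow-up period". That sentence concerns related adverse events, however. The SAE percentage comes in a later sentence without that limit.

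A third argument is that Protocol 7 and 7.4.2 use looser wording, under which serious events and related events might be two groups. The word *both* in 7.2 and 7.3 settles the meaning. If some sites nevertheless followed the looser reading, the row would mix two capture rules, which is no easier to interpret.

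Some stronger readings are tempting but not supported:

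- A reader might infer a large understatement. Assuming that 10% to 30% of patients have any SAE and 5% are captured gives 10/5 = 2-fold to 30/5 = 6-fold. Those rates are not in the documents, so the ratios are no estimate.
- A reader might infer that the related adverse-event summary can contain only serious events. The Seriousness field cited in SAP 8.3 has a not-serious option, and the Table 1 telephone footnotes refer to potential device-related adverse events without requiring seriousness. Non-serious events may therefore appear, but incompletely.
- A reader might infer that the SAP commits the sponsor to publishing an all-cause rate or comparing it with other embolics. Neither document plans that comparison for SAEs.

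**Conclusion.** The mismatch between collection and tabulation is real, and it is confined to one row of the safety summary. As a count of patients with a related SAE or death from any cause, the row is correct. As an overall SAE rate it can err only downward, by an amount that the documents do not allow one to estimate and that is zero if no patient has solely unrelated non-fatal SAEs. The gap is narrower than it may first appear, because possible and unassessable causality is captured; only non-fatal SAEs that the site judges not related are missed.

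The conclusion assumes that sites follow Protocol 7.2 and 7.3 as written. If some report unrelated SAEs as well, the row is less incomplete but inconsistent between sites. The primary and secondary endpoints are derived in SAP 8.2 and 8.3 without using this row and are not affected. This is a minor point, worth correcting before tables are produced.

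**What to change.** In SAP 8.4, replace the unqualified SAE row with two rows: *device- and/or procedure-related SAEs* and *deaths from any cause*. Alternatively, keep one row and relabel it *related SAE or death from any cause*. In either case:

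- Add a footnote that unrelated non-fatal SAEs and non-serious events were not systematically collected. Do not write that they were not collected at all, since some may be in the database.
- State which causality categories count as related in this table, given the different rules in SAP 8.3 and Protocol 7.2.

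The cost is SAP and table wording only, with no new data and no eCRF change. The downside is that the report will contain no overall SAE rate. If the sponsor wants one, the protocol and eCRF would have to be amended to collect all SAEs, which is a much larger change and is not needed to correct this point.
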